#### **4.2.3 Continuation of Investigational Therapy after Radiographic Progression (Pseudoprogression)**

Treatment may be continued in the setting of pseudoprogression (radiographic increase or new lesions felt to be due to inflammation/immune response) as long as all of the following criteria are met:

- Absence of clinical symptoms or signs indicating clinically significant PD.
- No significant decline in Eastern Cooperative Oncology Group (ECOG) performance status.
- Absence of rapid PD or threat to vital organs/critical anatomical sites (eg, spinal cord compression) requiring urgent alternative medical intervention
- Patients are made aware of the potential benefits and risks of continuing study therapy in the setting of Pseudo-Progression.

These patients will continue to be monitored for safety parameters. Patients continuing therapy in the setting of suspected pseudoprogression should continue with treatment according to protocol as long as the above criteria are met and clearly documented in the patient's medical record.

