## 5.0 STUDY PROCEDURES

	Screening (-28 days)	On Treatment 		Off Treatment	
Time Period	Baseline	Cycle 1+ (+/- 3days)	After Every 3 cycles	End of Treatment	Follow-up 
Assessment or Activity					
Informed Consent	X				
Medical history (H)	X			X	
Concomitant Medications 	X	X		X	X 
Vitals, Physical exam  (PE) 	X	X		X	
ECOG status	X	X		X	
Toxicity assessment 		X		X	X 
Tumor Measurements 	X		X 	X	
Biopsy/archival tissue 	X				
CBC with diff 	X	X		X	
Chemistry panel 	X	X 		X	
PT/PTT/INR 	X				
Thyroid function tests 	X		X 		
Pregnancy test 	X				
Pembrolizumab 		X			
Capecitabine 		X			
Survival status					X

 Every physical exam will be a full physical exam and is standard of care. It will include vital signs (pulse, temperature, and blood pressure) and height (baseline only) and weight.

 CT c/a/p AND bone scan. In place of bone scan, a PET/CT may be used. If CT is contraindicated, MRI may be used. Any additional imaging such as MRI can be completed at the physician's discretion. The same modality should be used throughout the study. The baseline procedure is to be performed within 28 days prior to registration. Subsequently, it will be done prior to the start of the next treatment cycle e.g 4, 7, 10 etc. For patients who are unable to obtain scans at the designated time points, a window of 7-10 days is allowed. This exception is not applicable to the screening period. Bone scans are to be repeated at each time point ONLY if the patient has bone metastasis or if it is clinically indicated. If the original bone scan during screening is negative, then bone scans are not required in subsequent visits.

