### **6.3 Endpoints**

#### **6.3.1 Primary Endpoint(s):**

To evaluate the median progression-free survival (median PFS) for participants receiving pembrolizumab with capecitabine for the treatment of locally advanced or metastatic TNBC and hormone-refractory MBC. This will be assessed by using RECIST 1.1 criteria.

**Complete Response (CR):** Disappearance of all target lesions. Any pathological lymph nodes (whether target or non-target) must have reduction in short axis to <10 mm.

**Partial Response (PR):** At least a 30% decrease in the sum of diameters of target lesions, taking as reference the baseline sum diameters.

**Progressive Disease (PD):** At least a 20% increase in the sum of diameters of target lesions, taking as reference the smallest sum on study (this includes the baseline sum if that is the smallest on study). In addition to the relative increase of 20%, the sum must also demonstrate an absolute increase of at least 5 mm. (Note: the appearance of one or more new lesions is also considered progression).

**Stable Disease (SD):** Neither sufficient shrinkage to qualify for PR nor sufficient increase to qualify for PD, taking as reference the smallest sum diameters while on study.

Please note patients with PD may stay on study with PD if they meet the criteria in section 4.2.3.

*Any patient who has completed **at least 3 cycles** of pembrolizumab and capecitabine will be evaluable for this endpoint.*

*Note: the first set of scans is required to establish that the patient is evaluable for this endpoint.*

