**QualTek Molecular Laboratories**  
**MISP Receiving**  
**[name]**  
**[name]**  
**[contact]**  
**Email: [[contact]](mailto:[contact])**

## 10.0 STATISTICAL CONSIDERATIONS

For PFS, assumptions are that the addition of pembrolizumab will increase PFS to 5  
months compared to historical control of 3 months. Assuming exponential survival, with  
27 evaluable patients, there is 80% power to detect this difference using a one-  
tailed z test at  $p < 0.05$ .

Recruitment of 30 participants to accrue 27 evaluable will last approximately 30 months  
(2.5 years) and participants will be followed for a maximum of 2 years from enrollment of  
the last patient. The primary outcomes chosen is PFS based on mechanism of action..

PFS will be analyzed using a Kaplan-Meier curve. A confidence interval for the median  
PFS will be calculated (Brookmeyer, R. and Crowley, J. (1982), "A Confidence Interval for  
the Median Survival Time," *Biometrics*, 38, 29-41.), and if the confidence interval is  
totally above 3 months, then it may be concluded that the PFS exceeds 3 months.

Objective response rate will be summarized using a proportion and an exact 95% binomial confidence interval. Anti-tumor activity will be reported as a percentage change in the sum of the dimensions of all measurable lesions as defined by RECIST 1.1 criteria. The baseline imaging before treatment will be compared to each subsequent imaging assessment. The maximum anti-tumor activity will be reported using the assessment with the smallest sum of dimensions (maximum response).

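### Maximum anti-tumor activity is taken from the smallest sum at any scan, with no cut-off at RECIST 1.1 progression, so this descriptive summary can show shrinkage that came only after progression

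*Combined protocol and SAP*

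**What the plan says.** Section 10.0 (Statistical Considerations) plans a summary of anti-tumor activity as a "percentage change in the sum of the dimensions of all measurable lesions as defined by RECIST 1.1 criteria". It then says which scans count: "The baseline imaging before treatment will be compared to each subsequent imaging assessment". The per-patient figure follows: "The maximum anti-tumor activity will be reported using the assessment with the smallest sum of dimensions (maximum response". Neither this section nor any other limits the choice to scans up to progression or before new therapy.

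Two other sections bear on which scans will exist. Section 4.2.3 provides: "Treatment may be continued in the setting of pseudoprogression (radiographic increase or new lesions felt to be due to inflammation/immune response", subject to four conditions on symptoms, performance status, speed and site of progression, and patient awareness. Section 6.3.1 repeats this beside the RECIST 1.1 definitions: "Please note patients with PD may stay on study with PD if they meet the criteria in section 4.2.3". The imaging footnote in section 5.0 places the on-treatment scans: "Subsequently, it will be done prior to the start of the next treatment cycle e.g 4, 7, 10 etc".

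On what counts as progression, section 6.3.1 requires a rise of at least 20% and at least 5 mm from the smallest sum on study, and adds that "the appearance of one or more new lesions is also considered progression".

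**The concern.** A best-change figure is normally read beside the response rate and PFS as a picture of how far tumors shrank before the disease progressed. Here the two can part company. A patient can meet RECIST 1.1 progression, stay on treatment under section 4.2.3, and have a smaller sum at a later scan. The rule in section 10 then picks the later scan and calls it that patient's maximum response, while the RECIST 1.1 analyses record progression at the earlier one. Shrinkage after progression belongs naturally with the exploratory irRECIST analysis in sections 2.3 and 6.3.3, but the section 10 rule lets it into the main summary unmarked.

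The amendment history (section 14.0) lists section 4.2.3 as added by Amendment 2 and lists no matching change to section 10, which may be how the gap arose.

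At stake is the reading of one descriptive display in a small single-arm trial (27 evaluable patients planned), where a few patients can change the visual impression.

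**Working it through.** The plan gives no figure for this summary, so there is none to reproduce. The check has three steps.

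**1. Can scans after progression occur?** Yes. Section 5.0 schedules imaging before cycles 4, 7, 10 and so on. With 21-day cycles, that is about every 3 × 21 = 63 days, or 9 weeks. A patient who continues under section 4.2.3 stays on that schedule; no text stops imaging at first progression. The schedule also marks tumor measurements at end of treatment, which can fall after the progression scan. It marks none in follow-up. The affected patients are therefore mainly those continued under section 4.2.3.

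**2. Which way does the rule err?** Let S₀ be the baseline sum and Sₜ the sum at scan t. The change at scan t is 100 × (Sₜ − S₀)/S₀. As written, the rule reports the minimum over all post-baseline scans. A rule cut at progression reports the minimum over scans up to and including first progression, which are a subset of the same scans. A minimum over a larger set cannot be higher than the minimum over its subset. The written rule therefore gives either the same value or deeper shrinkage.

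**3. How different can one patient look?** These are hypothetical patients with S₀ = 100 mm; the sums are illustrations, not trial data.

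| Patient | Sums after baseline (mm) | First progression | As written | Up to and including progression |
|---|---|---|---|---|
| A | 125, then 65 | 125: +25% and +25 mm from the smallest sum (100) | (65 − 100)/100 = −35% | (125 − 100)/100 = +25% |
| B | 70, 90, then 60 | 90: (90 − 70)/70 = +28.6% and +20 mm | (60 − 100)/100 = −40% | (70 − 100)/100 = −30% |
| C | 90 with a new lesion, then 60 | 90: new lesion | (60 − 100)/100 = −40% | (90 − 100)/100 = −10% |

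Patients A and B progress on the sum itself, so they do not depend on how new lesions are handled. Patient C assumes that the new lesion is outside the sum. That holds for a new non-measurable lesion; for a new measurable one the text leaves it open.

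**What cannot be calculated.** A trial-level figure needs the number of patients continued past progression and the share whose smallest sum comes afterwards. The documents give neither.

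**The case against.** The strongest case for leaving the text alone is that this summary is purely descriptive. It is not among the objectives in section 2 or the endpoints in section 6.3, and it carries no test or decision rule. The protocol deliberately allows treatment through suspected pseudoprogression, so describing the deepest shrinkage over all scans is a defensible choice. The group is narrow: treatment normally ends at progression (sections 4.1 and 4.5), other antineoplastic therapy is prohibited on treatment (section 4.4), and irradiated lesions may not be used in disease assessment (note to section 3.2.5). All of this stands and limits the weight of the point. It does not supply the missing cut-off, and a reader of the report could not tell which values came from after progression.

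Three further objections are right and bound what may be claimed:

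- A reader might infer that the sum ignores new lesions. The text does not settle this. Section 10 sums all measurable lesions rather than the target lesions of section 6.1.3, so a new measurable lesion might be included.
- A reader might take the RECIST 1.1 wording in section 10 to make the figure a RECIST response category, or to imply a time limit. It does neither; it says which lesions are measurable.
- A cut at progression does not remove every disagreement. Old lesions may be smaller at the very scan that shows a new one. Percentage change and response category measure different things, which is why such patients should be marked.

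**Conclusion.** The point holds as a modest one. Section 10 has no progression cut-off and the protocol itself generates scans after progression. For patients whose smallest sum falls after progression, the summary can show deeper shrinkage than was seen up to progression, and so can disagree with their RECIST 1.1 classification. The direction follows from the rule; the size is unknown.

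Two stronger readings are not supported. The first is that PFS or the response rate is inflated. PFS is analyzed by Kaplan-Meier under RECIST 1.1 and the response rate is a separate proportion with an exact interval; neither uses this rule. Nor must the displays disagree: they can, in a subset, if such patients occur.

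The second is a figure in percentage points, for instance 1/27 = 3.7 points per affected patient in the share reaching a 30% reduction. The plan names no such share for this measure. A patient already at that depth before progression would add nothing to it. Section 6.1 admits patients without measurable disease, who have no measurable sum, so 27 is not a safe denominator. Any range built on it would rest wholly on assumed rates.

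**What to change.** In section 10, define maximum anti-tumor activity as the smallest sum among assessments up to and including the first RECIST 1.1 progression, and before any new anti-cancer therapy. The therapy clause will rarely matter on the present schedule but closes the definition. Mark in the display each patient whose progression was by new or non-target lesions. Report change after progression separately, with the exploratory irRECIST analysis. While the paragraph is open, say whether the sum covers the target lesions of section 6.1.3 or all measurable lesions, and whether new ones enter it.

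The cost is a sentence or two of text. The scans and dates are already collected, and treatment and imaging schedules do not change. The downside is that the reported shrinkage may look slightly less favourable, and late shrinkage after pseudoprogression moves to the separate display. If the sponsor prefers to count all scans, the plan should say so and flag the values that come from after progression.

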## **11.0 STUDY MANAGEMENT**

### **11.1 Institutional Review Board (IRB) Approval and Consent**

It is expected that the IRB will have the proper representation and function in accordance with federally mandated regulations. The IRB should approve the consent form and protocol.

In obtaining and documenting informed consent, the investigator should comply with the applicable regulatory requirement(s), and should adhere to Good Clinical Practice (GCP) and to ethical principles that have their origin in the Declaration of Helsinki.

Before recruitment and enrollment onto this study, the patient will be given a full explanation of the study and will be given the opportunity to review the consent form. Each consent form must include all the relevant elements currently required by the FDA Regulations and local or state regulations. Once this essential information has been provided to the patient and the investigator is assured that the patient understands the implications of participating in the study, the patient will be asked to give consent to participate in the study by signing an IRB approved consent form.

Prior to a patient's participation in the trial, the written informed consent form should be signed and personally dated by the patient and by the person who conducted the informed consent discussion.

### **11.2 Amendments**

The Principal Investigator will formally initiate all amendments to the protocol and/or informed consent. All amendments will be subject to the review and approval of the appropriate local, institutional, and governmental regulatory bodies, as well as by Janssen Scientific Affairs. Amendments will be distributed by the lead institution (Northwestern) to all affiliate sites upon approval by the Northwestern University IRB.

### **11.3 Registration Procedures**

Patients may not begin protocol treatment prior to registration. All patient registrations will be registered centrally through the Clinical Research Office at Northwestern University before enrollment to study.

#### Registering a Patient to a Phase II Study

BEFORE a patient can be treated on study, please complete and submit the following items to confirm eligibility and receive a subject identification number:

- Eligibility eCRF (complete in NOTIS)
- Eligibility checklist (signed and dated by the treating physician – upload in NOTIS)
- Signed and dated informed consent document (upload in NOTIS)
- Pathology Report (upload in NOTIS)

The QAM will review the registration, register the patient, assign an identification number, and send a confirmation of registration to involved personnel.

Registration will then be complete and the patient may begin study treatment.

The QAM can be contacted at [[contact]](mailto:[contact]).

#### **11.4 Data Submission**

Once a subject is confirmed and registered to the study, eCRFs should be submitted according to the detailed data submission guidelines (provided in a separate document). Generally, for all phase II patients, data are due at the end of every cycle.

#### **11.5 Data Management and Monitoring/Auditing**

This study will be conducted in compliance with the Data Safety Monitoring Plan (DSMP) of the Robert H. Lurie Comprehensive Cancer Center of Northwestern University (please refer to Appendices for additional information). The level of risk attributed to this study requires high level monitoring, as outlined in the DSMP. The assigned QAM, with oversight from the Data Monitoring Committee, will monitor this study in accordance with the study phase and risk level. Please refer to the Appendices for additional data submission instructions.

#### **11.6 Adherence to the Protocol**

Except for an emergency situation in which proper care for the protection, safety, and well-being of the study patient requires alternative treatment, the study shall be conducted exactly as described in the approved protocol.

##### **11.6.1 Emergency Modifications**

Investigators may implement a deviation from, or a change of, the protocol to eliminate an immediate hazard(s) to trial subjects without prior IRB approval.

For any such emergency modification implemented, an IRB modification form must be completed within 5 business days of making the change, and the QAM must be notified within 24 hours of such change.

##### **11.6.2 Other Protocol Deviations**

All other deviations from the protocol must be reported to the assigned QAM using the appropriate form.

A protocol deviation is any unplanned variance from an IRB approved protocol that:

- Is generally noted or recognized after it occurs.
- Has no substantive effect on the risks to research participants.
- Has no substantive effect on the scientific integrity of the research plan or the value of the data collected
- Did not result from willful or knowing misconduct on the part of the investigator(s).

A protocol deviation may be considered an instance of Reportable New Information (RNI) if it: Has harmed or increased the risk of harm to one or more research participants.

- Has damaged the scientific integrity of the data collected for the study.
- Results from willful or knowing misconduct on the part of the investigator(s).
- Demonstrates serious or continuing noncompliance with federal regulations, State laws, or University policies.

Any deviation that would constitute an instance of Reportable New Information must be reported to the Northwestern IRB within 5 business days of knowledge or notification.

### **11.7 Investigator Obligations**

The Principal Investigator is responsible for the conduct of the clinical trial at the site in accordance with Title 21 of the Code of Federal Regulations and/or the Declaration of Helsinki. The PI is responsible for personally overseeing the treatment of all study patients. The PI must assure that all study site personnel, including sub-investigators and other study staff members, adhere to the study protocol and all FDA/GCP/NCI regulations and guidelines regarding clinical trials both during and after study completion.

The Principal Investigator at each institution or site will be responsible for assuring that all the required data will be collected, entered onto the appropriate eCRFs, and submitted within the study-specific timeframes. Periodically, monitoring visits may be conducted and the Principal Investigator will provide access to his/her original records to permit verification of proper entry of data. The study may also be subject to routine audits by the Audit Committee, as outlined in the DSMP.

### **11.8 Publication Policy**

All potential publications and/or data for potential publications (e.g. manuscripts, abstracts, posters, clinicaltrials.gov releases) must be approved in accordance with the policies and processes set forth in the Lurie Cancer Center DSMP. The assigned QAM will prepare a preliminary data summary (to be approved by the DMC) no later than 3 months after the study reaches its primary completion date (the date that the final subject is examined or receives an intervention for the purposes of final data collection for the primary endpoint). If the investigator's wish to obtain DMC-approved data prior to this point (or prior to the point dictated by study design), the PI must send a written request for data to the QAM which includes justification. If the request is approved, data will be provided no later than 4 weeks after this request approval. The data will be presented to the DMC at their next available meeting, and a final, DMC-approved dataset will be released along with any DMC decisions regarding publication. The investigators are expected to use only DMC-approved data in future publications. The investigators should submit a copy of the manuscript to the biostatistician to confirm that the DMC-approved data are used appropriately. Once the biostatistician gives final approval, the manuscript may be submitted to external publishers.

### 13.0 APPENDICES

#### Appendix 1: ECOG Performance Status

Grade	Description
0	Normal activity. Fully active, able to carry on all pre-disease performance without restriction.
1	Symptoms, but ambulatory. Restricted in physically strenuous activity, but ambulatory and able to carry out work of a light or sedentary nature (e.g., light housework, office work).
2	In bed <50% of the time. Ambulatory and capable of all self-care, but unable to carry out any work activities. Up and about more than 50% of waking hours.
3	In bed >50% of the time. Capable of only limited self-care, confined to bed or chair more than 50% of waking hours.
4	100% bedridden. Completely disabled. Cannot carry on any self-care. Totally confined to bed or chair.
5	Dead.

\* As published in Am. J. Clin. Oncol.: *Oken, M.M., Creech, R.H., Tormey, D.C., Horton, J., Davis, T.E., McFadden, E.T., Carbone, P.P.: Toxicity And Response Criteria Of The Eastern Cooperative Oncology Group. Am J Clin Oncol 5:649-655, 1982.* The Eastern Cooperative Oncology Group, Robert Comis M.D., Group Chair.

## Appendix 2: CONTRACEPTION (specifications for Pembrolizumab)

Pembrolizumab may have adverse effects on a fetus in utero. Furthermore, it is not known if pembrolizumab has transient adverse effects on the composition of sperm.

For this trial, male subjects will be considered to be of non-reproductive potential if they have azoospermia (whether due to having had a vasectomy or due to an underlying medical condition).

Female subjects will be considered of non-reproductive potential if they are either:

(1) postmenopausal (defined as at least 12 months with no menses without an alternative medical cause; in women < 45 years of age a high follicle stimulating hormone (FSH) level in the postmenopausal range may be used to confirm a post-menopausal state in women not using hormonal contraception or hormonal replacement therapy. In the absence of 12 months of amenorrhea, a single FSH measurement is insufficient.);

OR

(2) have had a hysterectomy and/or bilateral oophorectomy, bilateral salpingectomy or bilateral tubal ligation/occlusion, at least 6 weeks prior to screening;

OR

(3) has a congenital or acquired condition that prevents childbearing.

Female and male subjects of reproductive potential must agree to avoid becoming pregnant or impregnating a partner, respectively, while receiving study drug and for 120 days after the last dose of study drug by complying with one of the following:

(1) practice abstinence† from heterosexual activity;

OR

(2) use (or have their partner use) acceptable contraception during heterosexual activity.

Acceptable methods of contraception are‡:

Single method (one of the following is acceptable):

- intrauterine device (IUD)
- vasectomy of a female subject's male partner
- contraceptive rod implanted into the skin

Combination method (requires use of two of the following):

- diaphragm with spermicide (cannot be used in conjunction with cervical cap/spermicide)
  - cervical cap with spermicide (nulliparous women only)
  - contraceptive sponge (nulliparous women only)
  - male condom or female condom (cannot be used together)
- hormonal contraceptive: oral contraceptive pill (estrogen/progestin pill or progestin-only pill), contraceptive skin patch, vaginal contraceptive ring, or subcutaneous contraceptive injection

†Abstinence (relative to heterosexual activity) can be used as the sole method of contraception if it is consistently employed as the subject's preferred and usual lifestyle and if considered acceptable by local regulatory agencies and ERCs/IRBs. Periodic abstinence (e.g., calendar, ovulation, sympto-thermal, post-ovulation methods, etc.) and withdrawal are not acceptable methods of contraception.

‡If a contraceptive method listed above is restricted by local regulations/guidelines, then it does not qualify as an acceptable method of contraception for subjects participating at sites in this country/region.

Subjects should be informed that taking the study medication may involve unknown risks to the fetus (unborn baby) if pregnancy were to occur during the study. In order to participate in the study subjects of childbearing potential must adhere to the contraception requirement (described above) from the day of study medication initiation (or 14 days prior to the initiation of study medication for oral contraception) throughout the study period up to 120 days after the last dose of trial therapy. If there is any question that a subject of childbearing potential will not reliably comply with the requirements for contraception, that subject should not be entered into the study.

